**Clavien-Dindo Complication Grades:**

Grade	Definition
Grade I	Any deviation from the normal postoperative course without the need for pharmacological treatment or surgical, endoscopic, and radiological interventions Allowed therapeutic regimens are: drugs as antiemetics, antipyretics, analgetics, diuretics, electrolytes, and physiotherapy. This grade also includes wound infections opened at the bedside
Grade II	Requiring pharmacological treatment with drugs other than such allowed for grade I complications Blood transfusions and total parenteral nutrition are also included
Grade III	Requiring surgical, endoscopic, or radiological intervention
Grade IIIa	Intervention not under general anesthesia
Grade IIIb	Intervention under general anesthesia
Grade IV	Life-threatening complication (including CNS complications) requiring IC/ICU management
Grade IVa	Single organ dysfunction (including dialysis)
Grade IVb	Multiorgan dysfunction
Grade V	Death of a patient

**10. SAFETY****10.1 SPECIFICATION OF SAFETY PARAMETERS**

The Investigator is responsible for monitoring the safety of participants who have enrolled in the study. Safety assessments will be based on medical review of adverse events and the results of safety evaluations at specified time points as described in Section 8.7, Schedule of Events. Any clinically significant adverse events persisting at the postoperative follow-up appointment will be followed by the Investigator until resolution/stabilization or death, whichever comes first.

**10.2 DEFINITIONS****10.2.1 ADVERSE EVENT (AE)**

An adverse event is defined as any undesirable physical, psychological or behavioral effect experienced by a participant during their participation in an investigational study, in conjunction with the use of the investigational product, whether considered intervention-related (21 CFR 312.32 (a)). In general, this includes signs or symptoms experienced by the participant from the time of signing the informed consent to completion of the study.

AEs may include, but are not limited to:

- Subjective or objective symptoms spontaneously offered by the participant and/or observed by the Investigator or medical staff.
- Clinically significant laboratory abnormalities.
- A significant worsening of the participant's condition from study entry.
- Disease signs and symptoms and/or laboratory abnormalities existing prior to the use of

- the study treatment that resolve but then recur after treatment.
- Disease signs and symptoms and/or laboratory abnormalities existing prior to the use of the study treatment which increase in frequency, intensity, or a change in quality after treatment.

#### 10.2.2 SERIOUS ADVERSE EVENT (SAE)

An AE or suspected adverse reaction is considered "serious" if, in the view of either the Investigator or Sponsor-Investigator, it results in any of the following outcomes:

- Death,
- A life-threatening adverse event,
- In-patient hospitalization or prolongation of existing hospitalization,
- A persistent or significant incapacity or substantial disruption of the ability to conduct normal life functions, or
- A congenital anomaly/birth defect.
- Pancreatitis requiring hospitalization
- GI bleeding requiring hospitalization
- GI perforation requiring hospitalization
- Any procedure-related complication resulting in delay of surgery

Important medical events that may not result in death, be life-threatening, or require hospitalization may be considered serious when, based upon appropriate medical judgment, they may jeopardize the participant and/or participant may require medical or surgical intervention to prevent one of the outcomes listed in this definition. Examples of such medical events include:

- Allergic bronchospasm requiring intensive treatment in an emergency room or at home,
- Blood dyscrasias or convulsions that do not result in in-patient hospitalization, or
- The development of drug dependency or drug abuse.

#### 10.2.3 UNANTICIPATED PROBLEMS (UP)

The Office for Human Research Protections (OHRP) considers UPs involving risks to participants or others to include, in general, any incident, experience, or outcome that meets all of the following criteria:

1. Unexpected in terms of nature, severity, or frequency given (a) the research procedures that are described in the protocol-related documents, such as the IRB-approved research protocol and informed consent document; and (b) the characteristics of the participant population being studied;
2. Related or possibly related to participation in the research ("possibly related" means there is a reasonable possibility that the incident, experience, or outcome may have been caused by the procedures involved in the research); and
3. Suggests that the research places participants or others at a greater risk of harm (including physical, psychological, economic, or social harm) than previously known or recognized.

This study will use the OHRP definition of UP.

#### 10.2.4 SEVERITY OF EVENT

Due to the known safety profile of botulinum toxin and FDA-approval for endoscopic injection for achalasia, AEs grade 1-2 will not be collected during the study. For serious AEs (Grade 3 or higher), the Investigator will grade its severity using, when applicable, the current version of the

CTCAE v5.0. In the event of an AE for which no grading scale exists, the Investigator will classify the AE as defined below:

---

- Grade 1:** Mild; asymptomatic or mild symptoms; clinical or diagnostic observations only; intervention not indicated.
- Grade 2:** Moderate; minimal, local or noninvasive intervention indicated; limiting age-appropriate instrumental ADL
- Grade 3:** Severe or medically significant but not immediately life-threatening; hospitalization or prolongation of hospitalization indicated; disabling; limiting self-care ADL.
- Grade 4:** Life-threatening consequences; urgent intervention indicated.
- Grade 5:** Death related to AE.

---

*Note: a semi-colon indicates 'or' within the description of the grade.*

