## 2.2 SECONDARY OBJECTIVES AND ENDPOINTS

Secondary Objective	Endpoint	Start	End
Evaluate the safety of pre-operative BTX injection into the Sphincter of Oddi	Rate of serious adverse events following BTX injection defined as: pancreatitis requiring hospitalization, gastrointestinal hemorrhage or perforation, other events delaying time to surgery or receipt of surgery, or grade 3 or higher AEs attributable to BTX	Day of study intervention	30 days following surgery or study intervention or until date of surgery
Evaluate the efficacy of pre-operative BTX injection compared to no therapy for the prevention of all POPF	Rate of any POPF following distal pancreatectomy/RAMPS, defined by standard biochemical definitions of POPF per ISGPF criteria	Day of Surgery	Postoperative day 30

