### 8.1.5 ADVERSE EVENT EVALUATION

Toxicities and adverse experiences will be assessed using the [NCI CTCAE 5.0](#). Safety will be monitored by assessing physical examination, vital signs, body height (screening only) and weight as clinically indicated. Additionally, hematology, chemistry, coagulation, urinalysis, thyroid function, and pregnancy will be assessed as clinically indicated.

Adverse events will be monitored from the time the participant receives treatment on study. Participants will be instructed to report all AEs during the study and will be assessed for the occurrence of AEs throughout the study, including and up to 30 days. Due to the known excellent safety profile of botulinum toxin and FDA-approval for endoscopic injection for achalasia, AEs grade 1-2 will not be collected during the study. AEs Grade 3 or higher must be recorded on the source documents and eCRFs regardless of the assumption of a causal relationship with the study drug.

Abnormal laboratory values will only be recorded as an AE if determined to be clinically significant by the investigator.

For details on AE collection and reporting, refer to Section 10.

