## **8.5 FOLLOW-UP**

Participants will be followed for 30 days following distal pancreas resection for efficacy. For safety, patients will be followed for 30 days following BTX injection if no surgery occurs or 30 days after surgery, whichever is longer. A follow-up visit will occur 14 days ( $\pm$  7 days)- following hospital discharge, consistent with standard of care practices. Additionally, all subjects will be contacted by phone by the NSQIP Surgical Clinical Reviewer ([name]) or other study team member approximately 30 days following operation to collect standard NSQIP other study datapoints. If a participant is diagnosed with any BTX-related adverse event (of any grade), additional follow-up phone calls will be performed monthly for three months following BTX injection to ensure resolution at the end of BTX duration of action.

Subjects not undergoing pancreatectomy and those undergoing pancreatectomy greater than 6 weeks from the date of BTX injection will not be evaluable for assessing efficacy of the study intervention but will be evaluable for assessing safety. The 6 weeks timepoint is chosen because the maximal efficacy of BTX may begin to wane following this timepoint. In patients undergoing BTX injection but not undergoing planned pancreatectomy (or experiencing a delay in pancreatectomy due to an AE from BTX), data on the reason(s) for delay or cancelled operation will be recorded.

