## 10.5 TIME PERIOD AND FREQUENCY FOR EVENT ASSESSMENT AND FOLLOW-UP

The occurrence of an UP, AE or SAE may come to the attention of study personnel during study visits and interviews of a study participant presenting for medical care, upon review by a study monitor, or during an audit. All AEs grade 3 or higher but not meeting the criteria for SAEs will be captured on the appropriate CRF. AEs of grade 1 and 2 will not be captured due to the well-characterized side effect profile of BTX for other indications, including endoscopic BTX injection which is FDA approved. Information to be collected includes event description, time of onset, clinician's assessment of severity, seriousness, expectedness, relationship to study product (assessed only by those with the training and authority to make a diagnosis), and date of resolution/stabilization of the event. All AEs grade 3 or higher occurring while on study must be documented appropriately regardless of relationship. All AEs will be followed to adequate resolution.

Any medical condition that is present at the time that the participant is screened will be considered as baseline and not reported as an AE. However, if the study participant's condition deteriorates at any time during the study, it will be recorded as an AE after treatment with study intervention begins.

Changes in the severity of an AE will be documented to allow an assessment of the duration of the event at each level of severity to be performed. AEs characterized as intermittent require documentation of onset and duration of each episode.

At each study visit, the Investigator will inquire about the occurrence of AE/SAEs since the last visit. Events will be followed for outcome information until resolution or stabilization.

The Investigator will record all reportable events with start dates occurring after treatment with study intervention begins for 30 days (for AEs grade 3 or higher) after the intervention is performed or 30 days after date of surgery, whichever is longer. AEs will be evaluated using the current version of the [CTCAE v5.0](#). At each study visit, the investigator will inquire about the occurrence of AE/SAEs since the last visit. Events will be followed for outcome information until resolution or stabilization. Any SAE that occurs after treatment with alternative therapy

will be reported only if the Investigator or current treating physician has assessed the SAE as related to the study treatment.

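### Section 10.2.4 ties seriousness to grade 3 or higher and three sections decline grade 1-2 AEs, but the SAE definition (10.2.2) and the safety endpoint (2.2) count events that delay surgery with no grade limit

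*Combined protocol and SAP*

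**What the plan says.** All references are to the combined protocol and SAP.

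**What is to be counted.** Section 2.2 makes the rate of serious adverse events after BTX injection the only secondary safety endpoint. Besides pancreatitis with admission and gastrointestinal bleeding or perforation, its list ends "other events delaying time to surgery or receipt of surgery, or grade 3 or higher AEs attributable to BTX". Section 10.2.2 defines an SAE by outcome, sets no grade, and includes "Any procedure-related complication resulting in delay of surgery". Section 11.4.2.1 reports the SAE rate in the safety set with a 95% confidence interval.

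**What is to be collected.** Section 10.2.4 reads "For serious AEs (Grade 3 or higher), the Investigator will grade its severity using". Section 8.1.5 says that, given the approval for "endoscopic injection for achalasia, AEs grade 1-2 will not be collected during the study", and section 10.2.4 repeats the rule. Section 10.5 says "AEs of grade 1 and 2 will not be captured due to the well-characterized side effect profile of BTX for other indications" and describes the recording window as "for 30 days (for AEs grade 3 or higher) after the intervention is performed" or after surgery, whichever is longer.

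**Text that points the other way.** Section 10.5 also says "All AEs grade 3 or higher but not meeting the criteria for SAEs will be captured on the appropriate CRF", which treats grade and seriousness as separate. Section 8.5 asks for the reason when surgery is cancelled, or for patients "experiencing a delay in pancreatectomy due to an AE from BTX". It also schedules monthly calls for BTX-related AEs whatever their grade. Section 8.1.4.1, under vital signs, sends significant new findings to the AE form with no grade limit. Section 11.4.4 summarises SAEs separately from grade 3-4 AEs.

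**The concern.** Seriousness (what the event led to) and severity (its grade) are different attributes, and the endpoint is built on the first. If collection is filtered on the second, an event can qualify for the endpoint and never reach the AE form.

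The exposed event is a grade 1-2 complication, handled without admission, that postpones or cancels the pancreatectomy. It is not far-fetched: section 1.3.1 says that the only side-effects previously reported for this injection are symptom-free lipase rises and mild pancreatitis. Delayed or lost surgery is also one of the harms that the safety endpoint was written to capture. As the text stands, whether such an event is counted depends on which section the investigator follows.

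**Working it through.** The plan states no expected SAE rate, so there is no figure of its own to reproduce. The check is a comparison of rules, followed by the size of one missed event.

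**Step 1: does the endpoint carry a grade limit for delay events?** In section 2.2 the grade 3 limit sits in the last item of the list, joined by 'or' to the item on delayed or lost surgery. It therefore qualifies only the BTX-attributable AEs. The synopsis also lists events that delay or prevent surgery without a grade. Section 10.2.2 has no grade in any criterion. So the answer is no.

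**Step 2: does the collection rule carry an exception?** In sections 8.1.5, 10.2.4 and 10.5 the statement that grade 1-2 AEs are not collected stands without an exception for SAEs or endpoint events. Section 10.2.4 goes further by writing serious and grade 3 or higher as equivalent.

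**Step 3: apply both to one case.** Take a grade 2 procedural complication, with no admission, that postpones surgery.
- Section 2.2: endpoint event.
- Section 10.2.2: SAE.
- Sections 8.1.5, 10.2.4 and 10.5, read literally: not collected.

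If the same event cancels surgery, it remains an endpoint event under 2.2, which covers receipt of surgery as well as its timing. The two sets of rules cannot both be followed.

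**Step 4: size of one missed event.** The denominator is the safety population, at most 55 injected (synopsis and section 11.2). The count of one event is an assumption. Section 11.4.2.1 does not name the interval method; the exact (Clopper-Pearson) interval is used here.
- One event counted: 1/55 = 1.82%. Lower limit 1 - 0.975^(1/55) = 0.05%; upper limit 9.72% (the 97.5% point of a beta distribution with parameters 2 and 54).
- Event missed: 0/55 = 0%. Lower limit 0; upper limit 1 - 0.025^(1/55) = 6.49%.
- Difference: 1.8 percentage points in the estimate, and 9.72 - 6.49 = 3.2 points in the upper limit.

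**Step 5: does anything else move?** The two-stage rule uses crPOPF only. Its stated figures (probability of early termination 0.787, expected sample size 30.33, power 0.876) reproduce by exact binomial calculation, and none uses an SAE count. The run-in rule in 11.4.5 counts surgical delays of 14 days or more and admissions for pancreatitis directly, without reference to AE grade.

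**The case against.** The strongest reply is that the parenthesis in 10.2.4 is loose drafting in a paragraph about severity grading, and that 10.2.2 is the governing definition. Section 10.5 separates grade 3 events that are not SAEs from SAEs, 10.6.2 asks sub-sites to report any SAE, and 11.4.4 tabulates SAEs apart from grade. On that reading only non-serious grade 1-2 AEs are left out. Section 8.5 also presupposes that low-grade BTX events are noticed, and delays show up in the injection-to-surgery interval needed for efficacy evaluability.

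Much of this stands, and it is why loss is a possibility and not an expectation. It does not remove the conflict: the three collection sections contain no exception, and nothing says that an 8.5 record feeds the 2.2 endpoint.

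Three stronger readings are tempting and are not supported.
- A reader might infer that cancelled surgery falls outside the endpoint because 10.2.2 names only delay. Section 2.2 itself counts it.
- A reader might infer that a delay caused by the endoscopy rather than by BTX is unprotected because 8.5 does not name it. It is an SAE under 10.2.2, and a second record is not required.
- A reader might want a probability that an event is missed. The documents give no rate for low-grade complications that delay or cancel surgery. Table 3 (163 events in 73,029 procedures, 0.22%) covers endoscopy events of all kinds. Any such figure would be the chance that an event occurs under an assumed rate, not the chance that it goes uncounted.

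**Conclusion.** The text is wrong as written: the collection rule, followed literally, drops events that the only secondary safety endpoint is defined to count. The conflict itself is certain from the wording. That an event would be lost in practice is only possible, given sections 8.5, 8.1.4.1, 10.5 and 11.4.4.

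The consequence is small and limited to one descriptive rate. Its size rests on two assumptions, that 55 are injected and that one event is missed. Even so, one missed event is the difference between a report of one SAE and a report of none.

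The finding does not call for collecting all grade 1-2 AEs. Low-grade events that meet no SAE criterion and leave the surgery date alone are outside the endpoint by design.

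**What to change.** 1. In 10.2.4, drop the grade parenthesis so that the sentence on severity grading begins: *For all collected AEs*.
2. In 8.1.5, 10.2.4 and 10.5, qualify the exclusion: *Grade 1-2 AEs are not collected unless they meet an SAE criterion in 10.2.2 or delay or cancel the planned surgery (2.2).*

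The cost is a wording change in three sections and a few more events to record. No visit, test or sample-size figure changes, and the light AE collection that the sponsor wants is otherwise kept.

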#### 10.2.5 ASSESSMENT OF CAUSALITY RELATIONSHIP TO STUDY INTERVENTION

For all collected AEs, the clinician who examines and evaluates the participant will determine the AE's causality based on temporal relationship and his/her clinical judgment. The degree of certainty about causality will be graded using the categories below:

- Definitely Related:** There is clear evidence to suggest a causal relationship, and other possible contributing factors can be ruled out.
- Possibly Related:** There is some evidence to suggest a causal relationship.
- Unrelated:** The AE is completely independent of study intervention administration, and/or evidence exists that the event is definitely related to another etiology.

#### 10.3 EXPECTEDNESS

The Investigator will be responsible for determining whether an AE is expected or unexpected. An AE will be considered unexpected if the nature, severity, or frequency of the event is not consistent with the risk information previously described for the study agent.

#### 10.4 ADVERSE EVENT LIST(S)

##### 10.4.1 ADVERSE EVENT LIST FOR BTX

Please refer to package insert for onabotulinumtoxinA for additional details.

Clinical Studies Experience: BTX (onabotulinumtoxinA) and BTX Cosmetic contain the same active ingredient in the same formulation, but with different labeled Indications and Usage. Therefore, adverse events observed with the use of BTX Cosmetic also have the potential to be observed with the use of BTX and vice-versa. In general, adverse events occur within the first week following injection of BTX and while generally transient, may have a duration of several months or longer and include:

Localized pain, infection, inflammation, tenderness, swelling, erythema, and/or bleeding/bruising may be associated with the injection. Needle-related pain and/or anxiety may result in vasovagal responses (including e.g., syncope, hypotension), which may require appropriate medical

therapy. Local weakness of the injected muscle(s) represents the expected pharmacological action of botulinum toxin. However, weakness of nearby muscles may also occur due to spread of toxin.

**Post-Marketing Experience:** There have been spontaneous reports of death, sometimes associated with dysphagia, pneumonia, and/or other significant debility or anaphylaxis, after treatment with botulinum toxin. There have also been reports of adverse events involving the cardiovascular system, including arrhythmia and myocardial infarction, some with fatal outcomes. Some of these patients had risk factors including cardiovascular disease. The exact relationship of these events to the botulinum toxin injection has not been established. New onset or recurrent seizures have also been reported, typically in patients who are predisposed to experiencing these events. The exact relationship of these events to the botulinum toxin injection has not been established. The following events, not already addressed elsewhere in the package insert, have been reported since the drug has been marketed: abdominal pain; anorexia; brachial plexopathy; diarrhea; facial palsy; facial paresis; hyperhidrosis; hypoacusis; hypoesthesia; localized numbness; malaise; myalgia; paresthesia; pyrexia; radiculopathy; skin rash (including erythema multiforme, and psoriasisiform eruption); tinnitus; vertigo; visual disturbances; and vomiting. Because these events are reported voluntarily from a population of uncertain size, it is not always possible to reliably estimate their frequency or establish a causal relationship to botulinum toxin.

#### 10.4.2 ADVERSE EVENT LIST FOR ENDOSCOPY

Overall, the rate of serious adverse events following endoscopy is less than 0.01%. Known risks associated with endoscopy are summarized in Table 3 have been extensively reported in large observational studies.

**Table 3. Adverse Events Associated with N=73029 Endoscopic Procedures**

Adverse event	Total	Percentage
Bleed	51	0.07
Cardiorespiratory arrest	21	0.03
Postprocedural pain	20	0.03
Pancreatitis	17	0.02
Arrhythmias	8	0.01
Febrile reaction	6	0.01
Non-cardiac chest pain	6	0.01
Perforation	5	0.01
Hypoxia	4	0.01
Iatrogenic	4	0.01
Hemodynamic	3	<0.01
Myocardial infarction	2	<0.01
Miscellaneous	2	<0.01
Obstruction	2	<0.01
Tooth break	2	<0.01
Anaphylaxis	1	<0.01
Aspiration pneumonia	1	<0.01
Cognitive dysfunction	1	<0.01
Dyspnea	1	<0.01

GI obstruction	1	<0.01
Seizures	1	<0.01
Sore throat	1	<0.01
Stricture	1	<0.01
Stridor	1	<0.01
Syncope	1	<0.01
Total	163	0.22

